#### 6.1.1.3 Definition of Maximum Tolerated Dose

The MTD is defined as the dose at which  $\leq 1$  of 6 patients experience a DLT, with the next higher dose having at least 2 patients experiencing a DLT.

Rules for Determination of MTD	
Number of Patients Experiencing DLT During Study Treatment	Action
0/3	Escalate to the next higher dose level.
1/3	Up to 3 additional patients will be added before treating patients at a higher dose. If none of the additional patients experience a DLT, the dose will be escalated. If one of the additional patients has a DLT, the MTD will have been exceeded and 3 additional patients will be added at the previous dose to determine the MTD and recommended Phase 2 dose.
2/3	If 2 of the first 3 patients at a dose level experience a DLT, the MTD will have been exceeded and 3 additional patients will be added at the previous dose to determine the MTD and recommended Phase 2 dose.

DLT = dose-limiting toxicity; MTD = maximum tolerated dose.

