**3 STUDY DESIGN**

**3.1 Summary of Study Design**

This is a Phase 1/2, open-label study of NS-018 in patients with PMF, post-PV MF, or post-ET MF. Patients in the first cohort will self-administer NS-018 orally at a starting dose of 75 mg daily. Doses will be increased in later cohorts based on safety data. Treatment will be administered continuously as daily therapy in cycles of 28 days in duration.

Approximately 24 patients will be enrolled during the Phase 1 portion (treated with escalated doses in a standard 3+3 cohort design) and 20 patients will be enrolled during the Phase 2 portion (treated at the MTD). Consideration by the Safety Review Committee will also be given to suspending Phase 2 enrollment at the MTD, and instead adding the same total number of patients at a second dose level, the CAD. The expansion cohorts for the MTD and CAD, should they both be pursued, will not be concurrently open for enrollment. The two dose levels would instead be expanded sequentially. Consideration will also be given to enroll patients only at the CAD but not MTD level, based on the risk/benefit of therapy as judged by the investigator/medical monitor and sponsor.

For the purpose of scheduling procedures and evaluations, a treatment cycle is defined as 28 days. A patient may continue to receive treatment with NS-018 until the patient experiences unacceptable toxicity that precludes any further treatment, disease progression, and/or as long as the patient is benefiting from treatment, at the discretion of the investigator.

This study will be conducted at selected sites in the United States.

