**6 TREATMENT AND RESTRICTIONS**

**6.1 Treatment**

**6.1.1 Treatment Regimen, Dosage, and Duration**

Patients will be treated at the dose cohort level to which they are assigned. All study drug will be self-administered orally. NS-018 will be self-administered 2 hours or more after the last meal and at least 1 hour before the next meal.

The dose levels planned and the numbers of patients in each dose level are presented below.

Once Daily (QD) Cohort [completed]			Twice Daily (BID) Cohort							
Cohort	NS-018 Total Daily Dose(mg)	No. of Patients Per Cohort	Cohort	NS-018 Total Daily Dose(mg)	No. of Patients Per Cohort					
Phase 1			Phase 1							
QD 1#	75	3-6								
QD 2#	125	3-6								
QD 3#	200	3-6	BID 1#	200 (100×2) £	3-6					
QD 4#	300	3-6		—	—					
	—	—	BID 2#	400 (200×2) £	3-6					
	—	—	BID 3#	600 (300×2) £	3-6					
	—	—	BID 4#§	800 (400×2) £	3-6					
Phase 2	MTD or lower Up to 20 patients									
MTD = maximum tolerated dose.										
£ BID dosing must be administered 12 hours apart										

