# If a DLT is experienced at any dose level, an intermediate cohort at a lower dose may be considered, as recommended by Safety Review Committee										
§ Additional cohorts at doses > 400 mg BID (800 mg/day) may be considered by the Sponsor if agreed by the Safety Review Committee after review of PK, PD, and safety data. The maximum planned increase in dose between cohorts will be 200 mg as the total daily dose (e.g., the dose level above 400 mg BID will not exceed 500 mg BID )										

During the study, a Safety Review Committee will review data from each cohort and may make dosing schedule changes based on the data review. The Safety Review Committee is described in detail in Section 13.9.

In the Phase 1 portion of the study, sequential cohorts of 3 to 6 patients will be treated with escalating doses until the MTD is established (see Section 6.1.1.3). The first patient in each cohort must be observed for at least 7 days of dosing with NS-018. If there is no clinically significant toxicity observed in that patient, enrollment in the cohort may continue. If a significant toxicity occurs, including any possible dose-limiting toxicity (DLT, see Section 6.1.1.2), the Safety Review Committee must meet and determine whether additional patients may be entered at that dose or an intermediate cohort at a lower dose should be considered. Each cohort can be assessed after at least 3 patients have completed 28 days of study drug dosing.

The Safety Review Committee can make dosing schedule changes (twice daily dosing rather than once daily dosing; intermediate dose levels if toxicity occurs that does not rise to the level of a DLT) based on pharmacodynamic, pharmacokinetic, and safety review. If twice daily dosing requires evaluation, dosing would start at one total daily dose level below the last once per day dose level that was declared safe. For example, when 300 mg QD was declared safe,

the starting dose for BID dosing would be 100 mg twice daily, 12 hours apart [representing a total daily dose 200 mg]).

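### Both MTD-exceeded rules add 3 patients at the previous dose even when 6 have already been treated there

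*Combined protocol and SAP*

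**What the plan says.** Section 6.1.1.3 defines the MTD as the dose at which at most 1 "of 6 patients experience a DLT, with the next higher dose having at least 2 patients experiencing a DLT". The table below the definition gives the actions.

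- **0/3:** escalate.
- **1/3:** "Up to 3 additional patients will be added before treating patients at a higher dose". If none of them has a DLT, escalate. If one does, the MTD has been exceeded.
- **2/3:** the MTD has been exceeded.

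Both MTD-exceeded outcomes end with the same instruction: "3 additional patients will be added at the previous dose to determine the MTD and recommended Phase 2 dose". Neither depends on how many patients the previous dose already has.

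Two other places bear on the intended size. Section 6.1.1 says that "sequential cohorts of 3 to 6 patients will be treated with escalating doses until the MTD is established", and its dose table repeats 3 to 6 per cohort. Section 3.1 describes patients as "treated with escalated doses in a standard 3+3 cohort design", and Section 12.1 uses the same label. No section states that the 3 patients are added only if fewer than 6 have been treated at the previous dose.

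**The concern.** A fixed addition of 3 reaches the definition's denominator of 6 only if the previous dose holds exactly 3 patients. A dose cleared through the 1/3 row already holds 4, 5 or 6, and the cell would take it to 7, 8 or 9.

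The case of 6 matters most. Once the next dose has at least 2 patients with DLTs, a previous dose at 1/6 satisfies the definition and nothing remains to be determined. The cell nevertheless asks for 3 more patients there. If one of them has a DLT, the result is 2/9, which the protocol does not classify: it is neither at most 1 of 6 nor a pattern in the table. The MTD would then rest on judgment where a written rule was meant to decide, after up to 3 unneeded Phase 1 exposures.

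**Working it through.** The protocol gives no operating characteristics for the MTD rule, so there is no figure of its own to reproduce. The only computed figures, the Section 12.1 probabilities of at least one event in 20 Phase 2 patients, do not depend on this rule.

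**Rules side by side.** Suppose 300 mg BID clears at 1/3 then 0/3, and 400 mg BID then shows 2 DLTs in its first 3 patients.

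- Definition: 300 mg BID has 1 DLT in 6 and the next dose has 2, so 300 mg BID is the MTD.
- Table, 2/3 row: add 3 patients at 300 mg BID, giving 6 + 3 = 9.
- One further DLT gives 2/9 = 22%. This lies between 1/6 = 17%, which meets the definition, and 2/6 = 33%, which does not.

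**Inputs.** The escalation rules come from Section 6.1.1.3. The DLT rates are assumptions: *p* at the previous dose (10%, 20%, 30%) and *q* at the next dose (40%, with a range of 30% to 50%). Expansion is taken as the full 3 patients, and any cohort that does not clear counts as exceeding the MTD.

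**Formulas.**

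- A: clears with 3 patients = (1−p)³
- B: clears with 6 patients = 3p(1−p)² × (1−p)³ = 3p(1−p)⁵
- C: already at 6, given cleared = B / (A + B)
- D: at least 1 DLT in 3 added patients = 1 − (1−p)³
- E: next dose exceeded = 1 − [(1−q)³ + 3q(1−q)⁵] = 1 − (0.216 + 0.093) = 0.691 at q = 0.4 (0.506 at 0.3, 0.828 at 0.5)

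| Quantity | p = 10% | p = 20% | p = 30% |
|---|---|---|---|
| A | 0.729 | 0.512 | 0.343 |
| B | 0.177 | 0.197 | 0.151 |
| C | 0.196 | 0.277 | 0.306 |
| D | 0.271 | 0.488 | 0.657 |
| C × D | 0.053 | 0.135 | 0.201 |
| B × E, q = 0.4 | 0.122 | 0.136 | 0.104 |
| B × E × D, q = 0.4 | 0.033 | 0.066 | 0.069 |

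C × D is conditional on the previous dose having cleared and the next dose being exceeded. B × E and B × E × D count from the opening of the previous dose. Over all combinations of *p* and *q*, B × E runs from 0.077 to 0.163 and B × E × D from 0.024 to 0.082.

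As a cross-check over whole escalations, four assumed dose-toxicity curves with DLT rates from 5% to 50% over 4 or 5 doses were enumerated. Among stops that have a previous dose, that dose already held 6 patients in 22% to 26%. Expansion by only 1 or 2 patients, which the 1/3 row allows, was not quantified.

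**The case against.** The strongest reply is that the protocol, read as a whole, leaves one workable reading. Cohorts run until the MTD is established (Section 6.1.1), and Phase 2 begins when it is reached. Once the definition is met, the cell's stated purpose is spent. The 3+3 label and the 3-to-6 cohort size point the same way. Sites do not decide on expansion: the CRO assigns the dose cohort (Section 4.3) and the Safety Review Committee must review each cohort (Section 13.9), so a literal misreading would have to pass both. The committee already has wide discretion over doses. A dose that meets the definition would by default be expanded to 20 patients in Phase 2, so 3 more there is not exposure to a dose regarded as unsafe.

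Most of this stands as a limit on the weight of the point. It does not remove it. Those sections imply the condition but do not state it, and the operative table says otherwise in a protocol that asks to be followed exactly (Section 13.8). Committee oversight supplies no criterion for 2/9. The Phase 2 comparison is also imperfect: those patients must have had prior JAK2 inhibitor therapy (Section 4.1), the phases are analyzed separately (Section 12), and the selected dose may be the clinically active dose instead of the MTD.

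**Conclusion.** The concern holds as a minor inconsistency. The table lacks a condition that the definition requires, and on an ordinary 3+3 path the two give different instructions. Under the assumed rates and literal use of the cell, the chance of reaching that path from the opening of the previous dose is 10% to 14% at *q* = 40%. The chance of also ending with an unclassified DLT count is 3% to 7%. These figures illustrate size only, because they rest on assumed DLT rates, full expansion and literal compliance.

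Once-daily escalation is marked as completed in Section 6.1.1, so the rule now matters only for the twice-daily cohorts. No stated sample size or precision figure depends on it.

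**What to change.** In both MTD-exceeded cells of Section 6.1.1.3, replace the fixed addition with:

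> *If fewer than 6 evaluable patients have been treated at the previous dose, add patients there up to a total of 6. If 6 have already been treated with at most 1 DLT, that dose is the MTD and no further patients are added.*

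The word *evaluable* fits Section 6.1.2, where patients with under 80% compliance in the first month are left out of the cohort review and an additional patient is enrolled.

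The cost is one clause in each of two table cells. It adds no patients and, compared with the literal rule, may save up to 3 in Phase 1.

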#### 6.1.2 Compliance Control

Patient compliance will be monitored by assessing the tablet count from the drug packages returned at each visit. Patients will complete a study drug dosing diary daily that will document the time of day they took their study drug. Tablet counts will be compared by the site to the dosing diary to further assess compliance and aid patient education regarding compliance. Documentation on the electronic Case Report Form (eCRF) will account for patient compliance during each cohort. Patients will be instructed to return any unused study drug and packaging when attending clinic visits or if the patient is discontinued before the study is complete.

Patients who take  $<80\%$  of the expected prescribed regimen will be counseled on the importance of taking the study drug appropriately. If compliance is  $<80\%$  during the first month of therapy, the patient will be counseled, remain on study drug and will follow the study assessment schedule. The patient will be included in all final study analysis populations (See Section 12.2), however the patient will not be included in the data from each cohort that is reviewed by the Safety Review Committee to determine dosing schedule changes. In the event that a patient's compliance is  $<80\%$  during the first month of therapy, an additional patient will be enrolled in the cohort and their data will be included in the cohort review by the Safety Review Committee as well as in all final study analysis populations.

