#### 6.1.1.1 Dose Reductions/Delays

Patients who experience a DLT, as defined in Section 6.1.1.2, **must** have study drug administration interrupted: 1) when a Grade 4 drug related toxicity returns to  $\leq$ Grade 1 or to baseline within 4 weeks of study drug interruption, the investigator may recommence treatment, but at one dose level below that at which the toxicity occurred; 2) when a Grade 3 drug related toxicity returns to  $\leq$ Grade 1 or to baseline within 4 weeks of study drug interruption, the investigator may recommence treatment at one dose level below that at which the toxicity occurred, or after discussion with the medical monitor, at the same dose at which the toxicity occurred. Discussion on the appropriateness of the patient continuing in the study will also include an evaluation of the current clinical response.

At each step, the investigator must carefully evaluate the relevant risks and benefits to the patient of continued study participation. A second dose reduction can be considered by the investigator if a second significant toxicity occurs, to one further cohort dose below. Patients whose baseline dose has been reduced for toxicity cannot be dose escalated back to the prior dose.

Study drug administration may be interrupted for clinically significant toxicities of  $\geq$ Grade 1 that do not meet DLT criteria, at the discretion of the investigator. Once the toxicity has resolved to Grade 0 or 1, or to baseline level within 4 weeks of study drug interruption, study drug may be resumed at either the same dose or one dose level below, at the discretion of the investigator. Furthermore, subjects who experience Grade 4 life-threatening non-hematological toxicity will not be eligible for further treatment, unless reviewed by the Safety Review Committee and deemed appropriate for continued follow up and possible re-initiation of study drug.

Antidiarrheal or antiemetic therapy must be administered before interrupting therapy for Grade 1 or 2 nausea, vomiting, and/or diarrhea.

Patients whose dose is reduced will continue the regular schedule of assessments.

Patients requiring a  $>4$  week interruption in study drug administration should be withdrawn from the study, unless reviewed by the Safety Review Committee and deemed appropriate for continued follow up and possible re-initiation of study drug.

These guidelines for dose reductions or delays also apply to patients in Phase 2 who experience a drug related toxicity

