### **13.9 Safety Review Committee**

A Safety Review Committee, consisting of the actively recruiting investigators, the medical monitor overseeing the study for NS Pharma and a NS Pharma representative will meet to evaluate each cohort. If clinically significant toxicity occurs in the first patient in any cohort during their first 7 days of NS-018 dosing, the Safety Review Committee will meet and determine dosing for future patients. The Safety Review Committee must review each cohort before patients can be enrolled into the next cohort. The Safety Review Committee can make dosing schedule changes (twice daily dosing rather than once daily dosing; intermediate dose levels if toxicity occurs that does not rise to the level of a DLT) based on pharmacodynamic, pharmacokinetic, and safety review. If twice daily dosing requires evaluation, dosing would start at one total daily dose level below the last once per day dose level that was declared safe.

If DLTs are seen in the 75 mg cohort, a cohort, labeled -1 and dosed at 50 mg, may be considered by the Safety Review Committee. Cohorts at doses >400 mg BID(800 mg/day)may be considered by the Sponsor if agreed by the Safety Review Committee after review of PD, PK, and safety data. The maximum planned increase in dose between cohorts will be 200 mg as the total daily dose (e.g., the dose level above 400 mg BID will not exceed 500 mg BID).

Should BID dosing commence during the Phase I portion of the study, the SRC will meet after the last patient in that cohort has completed 28 days of dosing to assess the safety of that dosing schedule. Should the BID cohort be declared safe, the next BID cohort may begin. BID cohorts and QD cohorts may enroll simultaneously provided the previous lower dose of each cohort type has been declared safe by the SRC.

During the Phase 2 portion of the study, the Safety Review Committee will meet when a DLT-equivalent AE occurs, in order to determine whether additional patients may be enrolled at the same dose level or at a lower dose thereafter. In addition, the Safety Review Committee will meet when the number of patients who have completed Cycle 1 reaches 10 to review the pooled safety information to determine if further enrollment is warranted.

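### Section 6.1.2 can drop a patient with a DLT from the cohort data behind the 3+3 decision when first-month compliance is under 80%, while Section 6.1.1.3 counts DLTs with no compliance condition

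*Combined protocol and SAP*

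**What the plan says.** Section 6.1.2 measures compliance from returned tablets ("Patient compliance will be monitored by assessing the tablet count from the drug packages returned at each visit") and compares the counts with a daily dosing diary. Patients who take less than 80% "of the expected prescribed regimen will be counseled on the importance of taking the study drug appropriately". If this happens in the first month, the patient stays on drug and in all final analysis populations, but "the patient will not be included in the data from each cohort that is reviewed by the Safety Review Committee to determine dosing schedule changes". A replacement is then provided for: "an additional patient will be enrolled in the cohort and their data will be included in the cohort review by the Safety Review Committee". The section says nothing about a patient in this position who had a DLT.

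Section 6.1.1.3 sets the 3+3 actions in a table whose first column is "Number of Patients Experiencing DLT During Study Treatment". It carries no compliance condition. With 0/3 the dose escalates. With 1/3 up to three patients are added: "If none of the additional patients experience a DLT, the dose will be escalated". With 2/3 the MTD has been exceeded.

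Section 13.9 links the two: "The Safety Review Committee must review each cohort before patients can be enrolled into the next cohort".

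Section 6.1.1.1 requires dosing to be interrupted after a DLT. Section 12.2 defines safety, PK, PD and efficacy populations, but no set of patients evaluable for DLT.

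**The concern.** A patient with a DLT and compliance under 80% is counted by Section 6.1.1.3 and is missing from the data described in Section 6.1.2. The protocol does not say which section prevails. If the committee follows Section 6.1.2, the event leaves the tally and a new patient, who may have no DLT, takes the place.

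A cohort decision rests on three to six patients, so one replacement can change the action. The MTD is part of the Phase 1 primary objective (Section 2.1.1). Declaring a cohort safe also opens intrapatient escalation for earlier patients (Section 6.1.1), and the MTD is a candidate dose for up to 20 Phase 2 patients. The planned Phase 1 interim safety analysis comes only after the MTD has been established (Section 12), too late to correct a tally.

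**Working it through.** **Figures the plan states.** The only probabilities are in Section 12.1, for at least one event among 20 Phase 2 patients. 1 − (1 − p)^20 gives 64.2%, 87.8%, 96.1%, 98.8% and 99.9% at 5%, 10%, 15%, 20% and 30%, matching the table. They do not bear on Phase 1, for which no operating characteristic is given.

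**Inputs.** The 3+3 rule is from Section 6.1.1.3, assuming that exactly three patients are added after 1/3. The 80% threshold and the replacement are from Section 6.1.2. The documents give neither a true DLT rate p nor the shares of patients who fall under 80%, so these are assumed over a range. Write q = 1 − p. A dose is *cleared* if the rule allows escalation past it.

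**Step 1: one DLT patient replaced by a new patient at the same true rate, no further removals.**

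- True 1/3, DLT counted: clearance needs no DLT in the next three, q³.
- True 1/3, patient replaced: the count is 0/3 with probability q, otherwise 1/3 again, so q + p·q³.
- True 2/3, both counted: 0.
- True 2/3, one replaced: the replacement and then the three added patients must all be free of DLT, q·q³.

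| Assumed p | True 1/3, counted | True 1/3, replaced | True 2/3, counted | True 2/3, one replaced |
|---|---|---|---|---|
| 20% | 51% | 90% | 0% | 41% |
| 33% | 30% | 77% | 0% | 20% |
| 50% | 13% | 56% | 0% | 6% |

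At 33%, for example: 0.67³ = 0.301; 0.67 + 0.33 × 0.301 = 0.769; 0.67 × 0.301 = 0.202.

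These figures are conditional on a removal having happened. They do not say how often it happens.

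**Step 2: the net effect when both kinds of patient can be removed.** Let f be the share of DLT patients removed and g the share of non-DLT patients removed. The rate among counted patients is p′ = p(1 − f) / [p(1 − f) + (1 − p)(1 − g)], and the clearance probability is (1 − p′)³ + 3p′(1 − p′)⁵. At p = 33%:

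| f | g | p′ | Clearance |
|---|---|---|---|
| 0 | 0 | 0.330 | 43% |
| 0.10 | 0 | 0.307 | 48% |
| 0.25 | 0 | 0.270 | 56% |
| 0.50 | 0 | 0.198 | 71% |
| 0.25 | 0.10 | 0.291 | 51% |
| 0.50 | 0.10 | 0.215 | 68% |
| 0.10 | 0.10 | 0.330 | 43% |
| 0.05 | 0.10 | 0.342 | 41% |
| 0.10 | 0.25 | 0.371 | 36% |

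The sign depends only on whether f is above, equal to or below g. The documents give neither share.

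**Step 3: can an ordered interruption trigger the exclusion?** Only if withheld doses stay in the compliance denominator. In that case 22 of 28 daily doses is 78.6%, under the threshold, and 23 of 28 is 82.1%, over it. For twice-daily dosing, 44/56 = 78.6% and 45/56 = 80.4%. A loss of six days would therefore be enough. The denominator in Section 6.1.2 is not defined for withheld doses, so this route is possible but not established.

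**The case against.** **The exclusion may concern only changes of schedule.** Sections 6.1.1 and 13.9 explain such changes as a move from once to twice daily, or intermediate doses for toxicity short of a DLT. On that reading Section 6.1.1.3 alone governs DLT counts and nothing conflicts. This is a fair reading, but it does not close the gap. Section 6.1.1 also uses the same phrase, without that explanation, for the committee's general review of each cohort. Section 6.1.2 places the replacement in the cohort review itself, and no separate dataset for escalation is described.

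**The rule looks aimed at voluntary non-adherence.** Counseling and staying on drug fit poorly with the interruption required after a DLT. That stands as evidence of intent. Yet a patient who skipped tablets and also had a DLT is still excluded.

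**Withheld and skipped doses can be told apart.** Tablet counts alone do not separate them, but the diary comparison and the eCRF record of dosage changes (Section 13.2.1) could help. A reader might infer that every DLT drops out through its own mandatory interruption. The text does not support that, because counting withheld doses as missed is only one reading, and not the most natural one.

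**Other safeguards exist.** They are the 7-day rule for the first patient in a cohort, the option of an intermediate cohort after any DLT, recruiting investigators on the committee, the Phase 2 safety meetings, and Grade 3/4 summaries in the Safety Population. They make it more likely that the event is known, but none returns the patient to the tally.

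**The MTD need not be too high.** Patients who skip doses have less exposure and may have fewer DLTs, which would make f smaller than g. This objection stands in full.

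**Conclusion.** The inconsistency is real and should be fixed. Followed as written, Section 6.1.2 can take a DLT out of a cohort's tally, and one removal can change 2/3 to 1/3 or 1/3 to 0/3. Each such removal lowers the count for that cohort.

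A reader might go further and infer that the MTD is biased upward. The documents do not support this. The net direction is upward if DLT patients fall under 80% more often than others, for instance because toxicity makes them skip doses. It is zero if equally often and downward if less often. At an assumed 33% rate, the scenarios above run from 36% to 71% clearance, against 43% when every patient counts. Nothing in the documents shows that a DLT patient was excluded in the once-daily cohorts marked completed in Section 6.1.1.

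The figures assume independent patients with a common DLT rate and exactly three patients added after 1/3. The textual conclusion needs none of these assumptions. Confidence is medium, because the narrow reading of Section 6.1.2 remains arguable.

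**What to change.** - In Section 6.1.2, state that a patient with a protocol-defined DLT in the cohort review period stays in the cohort DLT count whatever the compliance, and that only patients without a DLT who are under 80% are replaced. Cross-refer to this in Section 6.1.1.3.
- State how ordered interruptions and dose reductions enter the compliance figure, using the diary and the eCRF record of dosage changes.
- Show the committee DLTs in all treated patients, flagged by evaluability. For the completed once-daily cohorts, tabulate them beside the counts that the committee used.

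The cost is a few sentences, one cross-reference and one table, from data already collected. The downside is a somewhat conservative count, because DLT patients are always kept while some non-DLT patients are replaced. With f = 0, g = 0.10 and p = 33%, p′ = 0.33 / (0.33 + 0.67 × 0.90) = 0.354 and clearance is 39% instead of 43%. A cohort may therefore expand or stop sooner.
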